There is no clear consensus regarding appropriate control conditions to use in alcohol reduction app (Staiger, O'Donnell, Liknaitzky, Bush, & Milward, 2020) or ApBM research (Kakoschke, Kemps, & Tiggemann, 2018). In designing our control condition, a primary consideration was controlling for the effect of self-monitoring, since the data collection aspects of AAT-App involve regular self-report of alcohol use, and such self-monitoring behaviours may themselves assist with reducing alcohol use (Michie et al., 2012). To control for this effect, and thereby ensure that we can specifically attribute any positive effects to the inclusion of ApBM training (and not merely the effects of the data collection, which may not be present in a final version of the app that would be implemented clinically), the control version of the app includes the same self-report requirements as the ApBM version. A second consideration was ensuring blinding: if participants in the control condition know they are in a control condition, this may bias outcomes both due to expectancy effects and due to differential rates of drop-out (as participants may be less likely to remain motivated to continue participating if they know they are not receiving an intervention). If control participants were only asked to self-report weekly alcohol use, it is likely they may guess they are not in an intervention condition and, as such we have included a weekly sham-training task (which also functions as an approach bias measurement task), so that participants in both conditions can be told they are completing an “attention control” task.

Aims and Hypotheses

We aim to determine whether providing the “active” version of AAT-App (including ApBM) to people accessing outpatient alcohol treatment from AOD services, is effective, relative to a minimal version of the app which does not include ApBM training, at reducing alcohol use, cravings, and severity of dependence. We also aim to test the psychometric properties of the mobile phone approach bias measure we developed, and whether engaging in AAT-App significantly reduces approach bias, relative to the minimal control condition. We also aim to explore user experiences of AAT-App’s, perceived alignment with treatment, and suggested improvements, using qualitative interviews in a subset of participants, to guide further future improvements to the app and its implementation.

We hypothesise that:

Primary outcome:

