Minimal (control) group: Control participants will receive a minimal version of AAT-App which does not include any ApBM training or picture selection component, and only includes the weekly alcohol consumption questions, a weekly AAT task, and the VAS craving measure. Upon opening the app for the first time, participants are informed that they will be using "an app designed to target their alcohol use and awareness". Instead, participants are told that the "brain-training" will involve completing one training task at the end of each week, and answering some questions about their weekly alcohol consumption.

After reading the opening page's instructions, participants will then complete the alcohol consumption questions, before completing the pre-training VAS, the AAT, and the post-training VAS. The VAS is included so that cravings can be monitored before and after completing the AAT, where participants can access additional support if they indicate that their cravings are extreme (i.e., through links to Counselling Online and the National Alcohol and Other Drug Hotline). At the end of week 1 (i.e., 7 days post-baseline) participants will receive a notification reminder to complete the weekly alcohol consumption questions, followed by the pre-training VAS, AAT and post-training VAS. This process is repeated at the end of each week throughout the intervention period (i.e., 14-, 21- and 28-days post-baseline).

Procedure: Staff at participating services will briefly describe the study to clients who they believe may meet eligibility criteria. To allow for blinding, no specific details will be provided regarding approach bias modification, and participants will merely be informed that the study tests "a new smartphone 'brain-training app'" that "involves doing brief game-like tasks on your phone each week for 4 weeks". Clients who are interested will be asked to sign a form providing consent for the treatment service to provide their phone number to research staff. In the event they are unable to sign the form (e.g., if not present in person due to a telehealth appointment), clients can give verbal consent for the clinician to sign the form on their behalf. Clinicians can also complete the form online via Qualtrics Plus, by scanning a QR code on the paper form which directs them to an online

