Participants will be required to indicate that they have read and understood the information and consent to participate. This will result in the remaining baseline questionnaires being displayed including items assessing gender, which AOD treatment service the participant is attending, type(s) of treatment being accessed, drugs of concern, date of commencement of the current episode of treatment, treatment goal (abstinence or moderation), SDS, CEQ-F, and ATOP quality of life items. They will also be required to enter their smartphone number, and are encouraged to enter additional contact details (e.g., name, email, other phone numbers, and postal address) to assist with ensuring follow-ups are completed, although this is not required.

Completing the Qualtrics survey will result in an email being automatically sent to researchers, who will access the list of access codes, select the first unused code, and send the download link and access code to the participant via SMS. The researcher will record which access code was sent to which phone number. Once participants have downloaded the app, they will be prompted to enter the access code, thus resulting in either the ApBM or minimal version of the app being installed on their phone. Participants in the active condition will view a short introductory animation explaining how the ApBM intervention works, while participants in the minimal condition will be onboarded through written text that ensures blinding is maintained (see details provided above). Participants will then be required to complete the baseline alcohol consumption questions, before completing the pre-training VAS craving measure, the AAT, and the post-training VAS craving measure. Participants in the active condition will then proceed to the image selection feature, where they will be prompted to upload or select 6 alcohol-related images and 6 positive images to be used in the ApBM training task. These participants will then complete the pre-training VAS craving measure, their first session of the ApBM task, and the post-training VAS craving measure.

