Participants in the active condition will be instructed to complete at least 2 sessions of the ApBM training task (approximately 3-5 minutes in duration) each week for the duration of the 4-week intervention period, though they can complete more sessions if they wish (via a "more training" option in the app's homepage). Participants in the minimal condition will not complete any ApBM sessions. At the end of each week throughout the intervention period (i.e., 7-, 14-, 21- and 28-days post-baseline) participants will complete the weekly alcohol consumption questions. Participants in

the minimal condition will also complete the AAT (preceded and followed by the VAS craving measure) immediately after the alcohol consumption questions at each 7-day timepoint (which they will be told is an “attention training task”, to maintain blinding), while participants in the active condition will only complete the AAT again at the 28-day post-baseline timepoint. There will be no limitation on concomitant care/interventions that participants can commence during the intervention period (or the following follow-up period).

After completing the 28-day post-baseline alcohol consumption questions and AAT, participants in both conditions will be provided with an in-app link to a post-test Qualtrics survey which includes SDS, CEQ-F, ATOP items, and ratings of the app’s acceptability. The questionnaire will also ask if they have undergone any residential/inpatient treatment (e.g., residential rehabilitation, withdrawal treatment, or hospitalisation) in the past 28 days and, if so, will ask how many days they spent entirely within residential treatment (i.e., with no opportunity to drink alcohol), whether any of these days were in the past week, and, if so, how many. Participants will be reimbursed with a \$20 supermarket voucher for completing the post-test Qualtrics survey within 1 week (the link will expire after this point).

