- **[if no to previous question]** What was your old mobile number (the one you originally used when signing up to the study)?

RECORDER OFF

RECORDER ON

SECTION B: INTERVIEW

[Main dot-points represent the primary interview questions, sub-dot-points represent suggested prompts or follow-up questions that may be used as appropriate]

- To start off, I'm interested in knowing about what kind of treatment you were getting for alcohol use when you decided to try AAT-App. Can you tell me about that?
 - How long had you been involved in that treatment?
 - How were those treatments going for you?
- And what made you want to try AAT-App?
 - Can you describe the concerns you had about your alcohol use when you decided to use AAT-App?
 - Can you describe what was going on in your treatment when you decided to try AAT-App?
- Tell me about your experience using AAT-App. How'd you find it?
 - What were the positives/negatives?
 - Any bugs or glitches that came up?
- How (or in what contexts) did you use the brain-training app?
 - Did you use it at any particular times or places?
 - Did you try using it for immediate craving relief/support when urges to drink arose and, if so, how did that go?
- Can you tell me about any effects that AAT-App had on your alcohol cravings or drinking?
 - *[If they felt it was helpful]* When did you notice it helping?
- Do you have any thoughts about how AAT-App combined with the treatment you were receiving?
- What was your understanding of how the brain-training is supposed to work?
 - What do you think about the information provided in the app about how the brain-training works (if you can remember it)?
 - What influence, if any, do you think that knowing the theory behind the brain-training has on how the app worked (or didn't work) for you?
- What images did you choose to use for the brain-training?
 - [prompt for information regarding both positive and alcohol images if they only describe one category]
 - Did you use your own photos, or the ones provided in the app?
 - *[If they used photos provided in the app]* What did you think of the photo options provided in the app? (Do you have any suggestions about changes to the options?)

- What guided your decision about which photos to use?
- Do you have any suggestions for how the app could be improved?
- Do you have any other thoughts or opinions about the app that you would like to share?

Conclusion

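### Onboarding differs by arm after randomisation, with the mechanism explained only to the active arm, and no planned measure shows whether expectancy is balanced

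*Combined protocol and SAP*

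**What the plan says.** Recruitment keeps the mechanism from everyone: under Procedure, "no specific details will be provided regarding approach bias modification". Once the access code has been entered and the arm is fixed, the same section separates the two groups. "Participants in the active condition will view a short introductory animation explaining how the ApBM intervention works", whereas "participants in the minimal condition will be onboarded through written text that ensures blinding is maintained". The section on the minimal (control) group describes the control text: participants are using "an app designed to target their alcohol use and awareness", with one brain-training task and some drinking questions each week. Procedure adds that controls are told the weekly AAT is attention training. No mechanism is described for them.

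The in-app baseline comes after this step: "Participants will then be required to complete the baseline alcohol consumption questions", followed by the baseline AAT.

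The Introduction explains the choice of control. It wants any benefit to be attributable to ApBM training specifically. It names expectancy and differential drop-out as biases that would arise if controls knew their condition, and it adds the weekly sham task "so that participants in both conditions can be told they are completing an" attention control task. Design & Setting calls the trial double-blind, participants included.

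The primary outcome is self-reported standard drinks per week at 4 weeks. The post-test survey covers "SDS, CEQ-F, ATOP items, and ratings of the app", plus inpatient days; the later surveys repeat the scales and add the AUDIT at 3 months. App acceptability includes four ratings of whether the app helped or worsened drinking and craving, which Data Analysis describes within each group. The Appendix 1 interview guide asks what influence "knowing the theory behind the brain-training has on how the app worked", but only about 20 active-arm participants are interviewed.

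**The concern.** The two arms receive different accounts of what their app does, in different formats, after randomisation. A person shown why a task should weaken the pull of alcohol may expect more from it than a person given a general description. Expected benefit can change both drinking and how it is reported. The primary outcome and every secondary outcome except the AAT approach bias score are self-reported, so a difference in expectancy could enter almost all of the results.

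The protocol justifies this trial by noting that the earlier uncontrolled study could not separate ApBM from non-specific factors. If expectancy differs by arm and is not measured, part of that ambiguity returns. The interview prompt shows that the team regards knowledge of the theory as a plausible influence, but it has no control comparison.

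**Working it through.** **1. Is balance of expectancy measured anywhere?**

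| Source | Content | Tests balance of expectancy? |
|---|---|---|
| Baseline survey | Demographics, treatment details and goal, SDS, CEQ-F, ATOP | No; precedes allocation |
| In-app baseline | Drinking calendar, craving VAS, AAT | No |
| Post-test, 1-month and 3-month surveys | Scales, inpatient days, acceptability (post-test only) | No expectancy or allocation item |
| Four perceived-effect ratings, day 28 | Both arms, described within group | No; real benefit and expectancy are mixed |
| Interview prompt | About 20 people, active arm only | No control comparison |
| Data Analysis | No blinding assessment planned | No |

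**2. The plan's own sample-size figure.** Participants gives 178 for 90% power at partial eta squared .01 with 4 repeated measures. Assume the GPower default correlation of 0.5, which the plan does not state. Then f² = .01/.99 = 0.0101, and λ = f² × N × m/(1 − ρ) = 0.0101 × 178 × 4/0.5 = 14.4, on 3 and 3 × 176 = 528 degrees of freedom. Power is 0.902, and 178 is the smallest even N that reaches 90%. Also 178/300 = 59.3%. The figure reproduces, and this point does not affect it.

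**3. Illustration of how a bias would act.** Take the day-28 comparison as a two-sample t-test at two-sided α = .05 (sidedness is assumed), with no true ApBM effect and a bias of d SD favouring ApBM. The documents give no value for d; 0.1 to 0.3 is an assumed range. The smallest observed difference reaching p < .05 is about 1.96 × √(4/N):

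- N = 178: 1.96 × √(4/178) = 0.29 SD
- N = 300: 1.96 × √(4/300) = 0.23 SD

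The chance of a significant result favouring ApBM is approximately Φ(d√(n/2) − 1.96), with n per arm. For d = 0.2 and n = 89 this is Φ(0.2 × 6.67 − 1.96) = Φ(−0.63) = 0.27. The noncentral t values are:

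| Assumed d | 89 per arm | 150 per arm |
|---|---|---|
| 0 | 2.5% | 2.5% |
| 0.1 | 9.7% | 13.6% |
| 0.2 | 26% | 41% |
| 0.3 | 51% | 74% |

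The right-hand column assumes no attrition from 300, whereas the plan allows for 178 retained.

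**4. What the illustration leaves out.** The main model tests group × time. Baseline drinking is reported after onboarding, so a constant reporting shift already present at baseline would cancel in that interaction. A shift that grows, or a real change in drinking driven by expectancy, would not cancel. For SDS, CEQ-F and ATOP the baseline is taken before the access code is sent. A shift created by onboarding would therefore be absent at baseline and would not cancel.

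**The case against.** The strongest reply is that controls are not left without a story. They are told that they have an alcohol-related brain-training app and that their weekly task trains attention. ApBM details are withheld at recruitment, the app was renamed, and the protocol was kept private until data collection ended. All of this stands. A reader might infer that expectancy operates in one arm only; the documents support a possible difference in degree.

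A reader might also infer that the double-blind description fails. It does not follow: learning how one's own app works reveals allocation only to someone who knows that the other version lacks it. The participant information sheet is not available here and the control text is not reproduced in full, so its credibility cannot be judged.

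Nor would a difference go wholly unseen. Perceived-benefit ratings are collected in both arms and could show a gap, and exploratory between-group tests of the uMARS scales are allowed. But the ratings come after 4 weeks of use and cannot separate belief from effect.

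The attention-control label in the Introduction concerns the AAT, which both arms complete, so it does not strictly contradict the animation. The wording should still be aligned. Gamified scoring, picture selection and the larger number of sessions belong to the intervention and the choice of comparator. They may add to differential expectancy, and the fix would not remove them.

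**Conclusion.** The point holds as a cheap improvement. Onboarding is asymmetric after randomisation, the protocol itself names expectancy as a bias to prevent, the primary outcome is self-report, and nothing planned shows whether credibility or expected benefit is balanced. Blinding is attempted but unverified.

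The size of any bias is unknown. The percentages above follow from assumed biases of 0.1 to 0.3 SD in the day-28 comparison. A reader might take them as an estimate of false-positive risk in this trial; the documents give no basis for that. They show only that, with these sample sizes, a modest bias would matter. Nor do the documents show that expectancy does differ between arms, only that it could and that the plan could not tell.

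**What to change.** 1. Give the control version an introduction matched in format and length, presenting its weekly task as attention training with a comparably credible rationale. Align the onboarding text under Procedure with the shared cover story in the Introduction.
2. Add one credibility or expected-benefit item in both arms, after the baseline drinking questions and baseline AAT and, in the active arm, before the first ApBM session. Asking straight after onboarding would put it ahead of the baseline drinking report and could prime the answers. Report it by arm.
3. If an allocation guess is wanted, put it at the end of the 3-month survey, after all outcomes. At day 28 it could prompt thoughts about allocation before the day-56 and day-112 assessments. Interpret it knowing that real benefit also drives guesses. With shares near 50%, the 95% half-width for the between-arm difference is 1.96 × √(2 × 0.25/89) = 15 percentage points at 89 per arm, and 11 at 150.
4. Report blinding as intended, with these data shown by arm. If items 1 to 3 can no longer be implemented, report instead that onboarding differed and that blinding was not assessed.

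The cost is one short animation and one or two items. A late guess will be subject to attrition. The ApBM task, the sample size and the primary analysis are unchanged.
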